Naltrexone and Bupropion Combination on Obese, Smoking
Patients With Schizophrenia

NCT02736474

2015.12.30.

The sample of 60 evaluable subjects will have 80% power to detect a 4.5 kg differential change in weight between treatment groups, which is seen as a clinically meaningful weight change over 24 weeks, and 6 kg as the estimate of standard deviation for NB treatment based on previously published data of NB in overweight and obese but otherwise healthy people over 6 months. Although the Apovian et al. study was 56 weeks in duration, the study had a midpoint analysis at 28 weeks which showed that almost all of the weight loss had already occurred, making this data useful for our power analysis. To achieve power=0.80, with a two-tailed significance level of 0.05, 30 subjects per treatment group will be required.

All analyses will be performed on an intent-to-treat basis. Analyses will be carried using a mixed model repeated-measures analysis of variance with fixed effects of visit, treatment group, baseline score, and visit x treatment and visit x baseline score interactions and random participant-specific intercepts and slopes. Potential confounding variables will be included as covariates. The effect of treatment on 24-week change from baseline will be determined by the estimated regression coefficient of the visit x group interaction term. Differences between the treatment groups on categorical variables will be analyzed using the Fisher exact test or Chi-square

test. Independent sample t tests will be used to compare group differences on continuous variables.

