Baseline visit: Eligible subjects will come to the clinic for the baseline assessment including: 1) height, weight and waist circumference; 2) Fasting blood samples for glucose, insulin, leptin, ghrelin, HbA1c, lipid profile, comprehensive metabolic profile, CBC, high sensitivity CRP, IL-6 and TNF- α ; 3) breath CO level; 4) smoking craving using the Visual Analogue Scale; 5) number of cigarettes smoked in the past week; 6) the Positive and Negative Syndrome Scale (PANSS), 7) the side effects questionnaire. On a separate day, subjects who participate in the imaging assessment will complete the brain MRI scans. Subjects will then receive the study drug (either combination medication or placebo). The randomization is based on a 1:1 ratio using permuted block randomization, stratified by imaging assessment participation. In addition, subjects will receive the first session lifestyle counseling.

Follow-up visits: Subjects will be followed at weeks 2, 4, then every 4 weeks to receive the study drug and the lifestyle counseling. Weight, breath CO, and possible side effects will be assessed during each visit. Waist circumference, scales, the clinical

symptoms assessment will be repeated every 4 weeks. Fasting blood samples for glucose, insulin, leptin, ghrelin, HbA1c, lipid profile, comprehensive metabolic profile, CBC, high sensitivity CRP, IL-6 and TNF- α will be repeated at weeks 12, 24. Those subjects who participate in the imaging assessment, will repeat the brain MRI scans at week 24.

Intervention: This is a randomized, double-blind, placebo-controlled study. Following screening and confirmation that inclusion and exclusion criteria are met, subjects will be treated with naltrexone sustained release 15mg once per day and bupropion sustained release 150mg once per day in the first two weeks. Then subjects take naltrexone 15mg twice per day and bupropion 150mg twice per day during the rest of the study. The dosing choice of NB is based on the efficacy and side effects of various dosing strategies reported in previous NB trials as well as the supply availability of both naltrexone and bupropion in China. Subjects will be maintained on the same antipsychotic at the same dose whenever possible during the study; however the subject's clinical well-being will determine antipsychotic dosing. Subjects will return to meet with an investigator every 2 weeks for the first 4 weeks, then every 4 weeks to review medical and psychiatric status. Compliance will be

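### The SAP reads the 24-week treatment effect from a visit-by-group coefficient without stating rows, visit coding or reference visit; with post-baseline rows that coefficient is not in general the week-24 difference

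*SAP*

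**What the plan says.** The analysis paragraph of the SAP specifies a repeated-measures mixed model with "fixed effects of visit, treatment group, baseline score, and visit x treatment and visit x baseline score interactions and random participant-specific intercepts and slopes". The treatment effect is then defined by one rule: "The effect of treatment on 24-week change from baseline will be determined by the estimated regression coefficient of the visit x group interaction term".

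The sample size paragraph of the SAP bases the trial on a "4.5 kg differential change in weight between treatment groups, which is seen as a clinically meaningful weight change over 24 weeks", with an SD of 6 kg and 30 subjects per group.

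The Protocol (Follow-up visits) gives the schedule: "Subjects will be followed at weeks 2, 4, then every 4 weeks". It adds: "Weight, breath CO, and possible side effects will be assessed during each visit". Up to week 24 that makes seven post-baseline weights, at weeks 2, 4, 8, 12, 16, 20 and 24.

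Neither document states whether the baseline weight is also a response row, whether visit is a factor or a number, or which visit is the reference. No week-24 contrast is defined.

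**The concern.** Reading a treatment effect from visit by group is right when baseline is a response row and the categorical reference visit, because the groups are then compared on their change since that row. This SAP instead enters baseline as a covariate with its own visit interaction, which usually means that only post-baseline rows are modelled. In that model part of the treatment effect can sit in the group main effect, and the interaction coefficient leaves that part out.

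At stake is which quantity is reported as the main result. Two analysts could both follow the SAP and report different figures because they coded visit differently, and the choice could be made after the data are seen. Neither figure need be the one on which the trial was sized.

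**Working it through.** **1. The plan's own figure.** With 4.5 kg, SD 6 kg and two-sided 0.05, the normal approximation gives n per arm = 2 × (1.960 + 0.842)² × 6² / 4.5² = 27.9, so 28; the t-test version gives 29. At 30 per arm the noncentrality is 4.5 / (6 × √(2/30)) = 2.905 and the t-test power is 0.815. The stated 30 per group reproduces, and it rests on the simple week-24 difference.

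**2. What the coefficient is.** Let D(t) be the baseline-adjusted group difference at week t. With post-baseline rows and 0/1 group coding:

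- *Categorical visit, week 2 as reference.* There are six interaction coefficients, not one. The week-24 coefficient is D(24) − D(2), and D(2) is the group main effect.
- *Categorical visit, week 24 as reference.* D(24) is the group main effect. The interaction coefficients are D(t) − D(24) for the other visits, and none of them estimates D(24).
- *Continuous visit.* The coefficient is a slope difference in kg per week. Multiplied by 24, a step the SAP does not state, it equals D(24) only for special shapes such as linear from zero.

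The rule is therefore right if baseline is a response row and the categorical reference. It is also right (after the × 24) if visit is continuous and the effect is linear from zero, or if week 2 is the reference and D(2) = 0. The SAP states none of these.

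**3. Size, by illustration.** The true D(24) is 4.5 kg throughout; the shapes are assumptions. The exponential path is D(t) = 4.5 × (1 − exp(−t/τ)) / (1 − exp(−24/τ)). With complete data and random intercepts and slopes, the fitted slope is the least-squares slope Σ(t − t̄)D(t) / Σ(t − t̄)², where t̄ = 86/7 = 12.29 and the denominator is 403.4.

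Example, τ = 8: D = 1.048, 1.863, 2.994, 3.679, 4.095, 4.347, 4.500. The week-2-reference target is 4.500 − 1.048 = 3.45 kg. The slope is 61.36 / 403.4 = 0.152 kg per week, and × 24 gives 3.65 kg.

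| Assumed path of the effect | Week-2 reference (kg) | Slope × 24 (kg) |
|---|---|---|
| Exponential, τ = 8 weeks | 3.45 | 3.65 |
| Exponential, τ = 12 weeks | 3.70 | 4.00 |
| Exponential, τ = 20 weeks | 3.89 | 4.25 |
| Linear from zero | 4.12 | 4.50 |
| Linear to week 16, 18, 20 or 22, then flat | 3.94 to 4.09 (4.5 − 9/p for a plateau at week p) | 4.67, 4.73, 4.77, 4.62 |
| None to week 2, then exponential, τ = 8 | 4.50 | 4.76 |
| None to week 2, then linear | 4.50 | 4.91 |

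**4. Power.** The documents give no variance components. Four assumed sets of SDs (intercept; slope over 24 weeks; residual) were used: (1; 5.7; 1.5), (2; 5.2; 1.5), (1; 5.5; 2.0) and (3; 4.8; 1.5). Each gives a week-24 SD of 5.8 to 6.0. Calculations use 30 per arm, no dropout and a noncentral t with 57 df.

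Example, set 1, τ = 8: the SD of week 24 minus week 2 is √((5.7 × 22/24)² + 2 × 1.5²) = 5.64, because the intercept cancels. The noncentrality is 3.452 / (5.64 × √(2/30)) = 2.37 and power is 0.645. For the week-24 contrast the SD is √(1² + 5.7² + 1.5²) = 5.98 and power is 0.82.

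| Path | Week-2 reference | Slope | Week-24 contrast |
|---|---|---|---|
| τ = 8 | 0.62–0.77 | 0.64–0.77 | 0.82–0.84 |
| τ = 12 | 0.68–0.82 | 0.72–0.84 | 0.82–0.84 |
| τ = 20 | 0.73–0.86 | 0.77–0.88 | 0.82–0.84 |
| Linear from zero | 0.78–0.90 | 0.82–0.92 | 0.82–0.84 |
| None to week 2, then exponential, τ = 8 | 0.84–0.94 | 0.86–0.94 | 0.82–0.84 |
| None to week 2, then linear | 0.84–0.94 | 0.88–0.95 | 0.82–0.84 |

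The intercept cancels from the interaction but not from the week-24 contrast, so a larger intercept SD favours the interaction. With SDs (4; 4.2; 1.5) the week-24 SD is still 6.0, yet τ = 8 gives 0.849 and 0.861 against 0.816 for the contrast. Simulation under no effect gave type I error of 0.043 to 0.054 for all three tests.

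**5. What the documents say about shape.** The SAP cites, for a 56-week study, a "midpoint analysis at 28 weeks which showed that almost all of the weight loss had already occurred". If the group difference follows the same course, the share of the week-56 effect present at week 28, (1 − exp(−28/τ)) / (1 − exp(−56/τ)), is 97%, 91% and 80% for τ = 8, 12 and 20, against 50% for a path linear to week 56. The remark favours flattening but does not fix the shape before week 24; linear to week 24 and then flat also fits. Separately, the Protocol (Intervention) has once-daily dosing in the first two weeks and twice-daily dosing after that. Week 2 therefore closes the lower-dose period, which may make D(2) small.

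**The case against.** The best defence is that post-baseline rows are an inference. The SAP does not state them, and its sentence speaks of change from baseline, which suits a model with baseline as response row and reference. A single coefficient alongside random slopes also fits continuous visit better than categorical. In that case the week-2-reference figures fall away and only a linearity assumption is left. This stands as far as it goes: the text is open to a reading under which the rule is correct. But the baseline covariate points the other way, and nothing in either document settles it.

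A second defence is that the consequences rest on assumed shapes and variances. That also stands. With no effect until week 2, which the titration makes more plausible, the week-2-reference coefficient is exactly right and no power is lost in any of the four variance sets.

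A reader might go further and infer that the coefficient always understates a flattening effect. It does not: for linear-then-flat paths slope × 24 is too large (4.62 to 4.77 kg), while the week-2-reference figure for the same paths is too small. Nor do the documents support the inference that the trial loses power. For τ = 20 in the fourth variance set, the interaction tests reach 0.858 and 0.884 against 0.833 for the contrast.

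**Conclusion.** The concern holds as a defect in how the effect is defined. If the model uses post-baseline rows, as its covariates suggest, the coefficient the SAP names is not in general the week-24 difference, and the analyst's coding decides what is reported. For a true 4.5 kg the illustrations run from 3.45 to 4.91 kg, so the error can go either way. They are examples, not bounds, and assume complete data.

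The documents do not show that the planned analysis is certainly wrong, that it is biased in one direction, or that the trial is underpowered. The algebra is firm; the size of the consequence is not, because the documents say almost nothing about trajectory and give no variance components. Type I error and the 30 per group are not in question. The sentence should be corrected because it defines the reported treatment effect.

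**What to change.** Replace the sentence in the SAP's analysis paragraph with:

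> Visit is a categorical factor over the post-baseline visits (the random slope uses week as a continuous variable); the treatment effect is the model-based (least-squares mean) difference between groups at week 24, with its 95% CI and p-value.

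Categorical visit matters. With continuous visit, even the model-based week-24 difference is 5.00, 4.90 and 4.78 kg for τ = 8, 12 and 20 when the truth is 4.50 kg. Naming the contrast is also safer than giving a sum of coefficients, because such a sum changes with group coding: with −1/+1 coding the week-2-reference coefficient for τ = 8 is 1.726 in size instead of 3.452.

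If baseline was meant as a response row and the categorical reference visit, stating that instead also makes the coefficient the intended quantity.

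The cost is one SAP sentence and one contrast statement in the code, with no new data or patients. The week-24 contrast can have somewhat less power than the interaction coefficient if the effect is linear or delayed, and under some flattening curves when between-patient intercept variance is larger. In return, it targets the quantity on which the trial was sized.

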Naltrexone and Bupropion Combination on Obese, Smoking
Patients With Schizophrenia

NCT02736474

2015.12.30.

Subjects: A total number of 60 subjects will be recruited for the study with 30 of them to complete the imaging assessment. The major inclusion criteria are: 1) diagnosis of schizophrenia; 2) age between 18 and 65 years; 3) on stable antipsychotic medication regimen for at least one month; 4) BMI \geq 28 kg/m² using the BMI criterion for obesity in the Chinese population; 5) smoking at least 10 cigarettes daily for a minimum of 1 year; 6) desire to lose weight and quit smoking. The exclusion criteria are: 1) binge eating or other eating disorders; 2) current use of weight loss medications; 3) current substance use (except nicotine or caffeine); 4) elevated hepatic transaminase levels (>2.5x normal range); 5) clinically significant TSH and/or T4 abnormalities; 6) history of seizure disorder; 7) history of unstable cardiac problems or other unstable medication conditions; 8) being pregnant or nursing (for women).

Screening visit: After written informed consent is obtained, a diagnosis of schizophrenia will be determined by the International Classification of Diseases 10th Revision (ICD-10) by a research psychiatrist. A medical history and physical examination will be obtained by a research psychiatrist to assess inclusionary and exclusionary criteria, including current medications, substance use and number of cigarettes smoked daily. A urine pregnancy test will

be performed for women of childbearing potential. In addition, a urine drug screen, and a 12-lead EKG will be performed.

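### The SAP's only model cannot estimate its treatment effect for MRI, which has one follow-up scan; ANCOVA on the baseline scan should be named for it

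*SAP*

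**What the plan says.** The protocol (Subjects) plans 60 subjects, "with 30 of them to complete the imaging assessment". At the baseline visit, "subjects who participate in the imaging assessment will complete the brain MRI scans"; under Follow-up visits the scan is repeated once, at week 24. Randomisation is 1:1 and "stratified by imaging assessment participation", so the treatment comparison within the imaging subset is itself randomised.

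The SAP's analysis paragraph opens its method with "Analyses will be carried using a mixed model repeated-measures analysis of variance". The fixed effects are visit, group, baseline score, visit x group and visit x baseline, with "random participant-specific intercepts and slopes". "The effect of treatment on 24-week change from baseline" is then to be "determined by the estimated regression coefficient of the visit x group interaction term". No outcome is named, and nothing is said about outcomes with a single follow-up. The paragraph ends with a second rule: "Independent sample t tests will be used to compare group differences on continuous variables". That rule names no outcome, no scale (week-24 value or change) and no adjustment for baseline.

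**The concern.** The mixed model is built for outcomes measured repeatedly after baseline. Weight is one: it is taken at weeks 2, 4, 8, 12, 16, 20 and 24. MRI has a single post-baseline value, so the coefficient that the SAP uses to define the treatment effect does not exist for it.

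The model shows that baseline adjustment is intended, but the SAP does not say how to keep it when there is only one follow-up. The t test is the only other rule for continuous outcomes, and it makes no such adjustment. At stake are precision in a subset of about 15 per arm, and an analysis choice left open until the data are in hand.

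**Working it through.** **The plan's own figure.** The only power statement concerns weight: 4.5 kg difference, SD 6 kg, two-sided 0.05, 80% power, 30 per arm. The standardised difference is 4.5/6 = 0.75. A two-sample t calculation gives 28.9, so 29 per arm, and 30 per arm has 81.5% power. The stated figure reproduces. There is no corresponding figure for MRI.

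**Can the model be estimated for MRI?** Let g be group, b the baseline scan and v the visit time. The six fixed-effect columns are 1, v, g, b, v·g and v·b. With week 24 as the only outcome row, v = 24 for everyone, and the columns become 1, 24, g, b, 24g and 24b. Only 1, g and b are distinct, so the rank is 3. Visit is aliased with the intercept, visit x group with group, and visit x baseline with baseline. The random part has four parameters (intercept variance, slope variance, their covariance, residual variance), but one observation per subject supplies only one variance. For the weight schedule all four are identified.

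**What the alternatives can detect.** Inputs from the documents: n = 15 per arm (30 scanned, 1:1) and two-sided 0.05. The 80% power is the SAP's value for weight, carried over. Assumed, because the documents give neither: the correlation ρ between the two scans (0.5, 0.7, 0.8), and k = baseline SD divided by week-24 SD (1 in the main case). One scalar MRI measure and no missing scans are also assumed.

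In week-24 SD units, the detectable difference is λ × √(2V/n), where λ is the noncentrality giving 80% power:

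- Raw week-24 t test: V = 1, df = 2n − 2 = 28, λ = 2.902.
- Change-score t test: V = 1 + k² − 2ρk, df = 28, λ = 2.902.
- ANCOVA: V = (1 − ρ²)(1 + 1/(2n − 4)), df = 2n − 3 = 27, λ = 2.906.

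Example at ρ = 0.5, k = 1:

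- Change score: V = 1 + 1 − 1 = 1, giving 2.902 × √(2/15) = 1.060.
- ANCOVA: V = 0.75 × (1 + 1/26) = 0.779, giving 2.906 × √(2 × 0.779/15) = 0.937.

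| 15 per arm, k = 1 | ρ = 0.5 | ρ = 0.7 | ρ = 0.8 |
|---|---|---|---|
| Raw week-24 t | 1.06 | 1.06 | 1.06 |
| Change-score t | 1.060 | 0.821 | 0.670 |
| ANCOVA | 0.937 | 0.772 | 0.649 |
| Power of change-score t where ANCOVA has 80% | 70% | 75% | 77% |
| n per arm for change-score t to match ANCOVA at 15 | 19 | 17 | 16 |

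**Sensitivity.**

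- At ρ = 0.9 with equal SDs, the gain over change-score t is about 0.003 SD (0.474 against 0.471).
- With k = 1.25, change-score t gives 1.214, 0.955 and 0.795. The ANCOVA values do not depend on k, so the gain is larger.
- With k = 0.8, change-score t gives 0.971, 0.764 and 0.636. ANCOVA is then worse by 0.008 SD at ρ = 0.7 and by 0.013 SD at ρ = 0.8.
- With 12 scans per arm and k = 1, change-score t gives 1.20, 0.93 and 0.76; ANCOVA gives 1.06, 0.88 and 0.74.

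**The case against.** The SAP never assigns the mixed model to MRI, and its terms suit weight and the four-weekly scales. A reader might infer that the plan prescribes an impossible MRI analysis. The documents do not support that: the model is general, MRI is simply not mentioned, and the t-test sentence, read broadly, supplies a valid comparison within a randomised subset. This part of the objection stands. What is left is an unstated method and a loss of efficiency.

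It is also fair that dropping the aliased terms leaves group and baseline score, which is ANCOVA, so a careful analyst would probably get there. The SAP does not state that reduction, however, and its one alternative rule points to a different analysis.

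A second tempting inference is that the plan would inflate false positives for MRI, because someone might enter the baseline scan as a response as well as a covariate. The fixed effects then have full rank, but each baseline value is fitted exactly by its own covariate, and the variance model is degenerate. The SAP does not describe that set-up. A standard error from a fit that fails to converge would reflect the software, not an error rate of this plan.

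Finally, the gain in precision depends on assumed inputs, and under some of them a change-score t test is as good or slightly better. That stands too, and it limits the size of the point.

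**Conclusion.** The point holds as a minor one. The estimability result needs no assumption about the MRI data beyond one post-baseline scan with baseline as covariate: the SAP's named treatment effect cannot be estimated for MRI, and the only other written rule leaves the baseline scan unused as a covariate.

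The benefit of ANCOVA is conditional. With equal SDs and 15 per arm, the detectable difference falls by 0.12, 0.05 and 0.02 SD against change-score t at correlations of 0.5, 0.7 and 0.8: moderate at the low end, negligible by 0.9. Against a raw week-24 t test it falls by 0.12, 0.29 and 0.41 SD. If the baseline SD is clearly smaller than the week-24 SD, ANCOVA can lose about 0.01 SD to the change score. Nothing here bears on the weight analysis or the planned 60 subjects.

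**What to change.** Add one sentence to the SAP: each MRI measure is analysed in the imaging subset by ANCOVA of the week-24 value on treatment and baseline value, in place of the mixed model or the t test. Report the number of missing week-24 scans by arm, since ANCOVA, like the t test, uses only subjects who have that scan.

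Confine the change to MRI. The t-test sentence can stay as it is for other continuous variables; this point gives no ground for altering it there.

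The cost is SAP wording and 1 degree of freedom (27 instead of 28 with 15 per arm). The protocol already collects the baseline scan, so no data, visits or subjects are added.
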